9.2 Recording Adverse Events

9.2.1 Adverse Event Categorization

Reported Adverse Events will be categorized into one of the following two categories:

- 1. Primary Safety Endpoint: This category includes the 8 pre-specified adverse events that will be analyzed as the Primary Safety Endpoint for the study.
- 2. Other Adverse Events: This category includes all reported adverse events that meet the definition in Section 9.

The proposed categorization will serve to focus reporting, adjudicating, and analysis efforts to those categories most relevant for demonstrating the investigational device's relevant safety profile.

It is the intention of the Sponsor that AE's be collected in a uniform manner over the course of the study (independent of study arm) through the use of a Subject questionnaire. The Subject will be asked to complete a questionnaire regarding signs and symptoms experienced during each treatment. During regularly scheduled clinical follow-up visits during the trial, study staff will review the signs and symptoms noted by the Subject and provide education, as needed, on how they are documented. The study staff will determine whether subject reported signs and symptoms meet the definition of an AE as specified in Section 9. This approach attempts to eliminate any potential observed differences in AE rates between the study arms that are solely due to reporting sources or techniques.

Prior to analysis, all adverse events (AEs) will be coded using the Medical Dictionary for Regulatory Activities (MedDRA). Based on these coded terms, treatment emergent AEs will be summarized by treatment period, by severity, relation to procedure and relation to device.

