11.6 Analysis of Adverse Events

All study-emergent AEs occurring during the study sessions will be recorded and classified on the basis of MedDRA terminology for the ITT population. Study-emergent AEs are those AEs with an onset on or after the date of first study treatment. All study-emergent AEs will be categorized by study period (In-Center or In-Home), the number of Subjects reporting study-emergent AEs, severity, device relationship, and seriousness. Serious adverse events (SAEs) will be listed by Subject. SAEs will be categorized by study period, severity, and device relationship. Each Subject will be counted only once within a category using the event with the greatest device relationship and greatest severity.

For each treatment period, a 95% confidence interval will be computed on the pre-specified adverse event rate per dialysis interval. This confidence interval will be computed using the Least Square Mean for the respective treatment period from a generalized linear model containing terms for Subject, arm and time points (i.e., a repeated measures analysis using GEE) using a Poisson link function and AR(1) covariance structure.

Summary statistics (mean, sample size, standard deviation, minimum, maximum, median) will be computed on the number of pre-specified adverse events per dialysis interval for each treatment period. The same summary statistics will be calculated by treatment period for the rate of pre-specified adverse events per 100 dialysis treatments.

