4.2.3 Other Analyses

Analyses described in this section will be performed on the ITT population with no missing value imputation.

Clinically Significant Alarms

The number and percentage of treatments with each alarm type (air in venous lines, low systolic BP, high venous pressure, low venous pressure, blood leaks, and alarms ending treatment) will be reported by treatment period.

Summary statistics (mean, sample size, standard deviation, minimum, maximum, and median) on the number of alarms per subject will be provided by treatment period, time point, and treatment number for each alarm type.

Time to Resolve or Clear Alarms

Summary statistics (mean, sample size, standard deviation, minimum, maximum, and median) on the time to resolve/clear alarms will be provided by treatment period. All alarm types will be combined for this analysis. The denominator in the mean calculations will be the number of alarms in the respective treatment period.

Prescription Changes

The number of prescription changes made from initial input during each dialysis treatment will be summarized via summary statistics (mean, sample size, standard deviation, minimum, maximum, and median) for each treatment period and time point. The denominator in the mean calculations will be the number of treatments in the respective treatment period and time point.

The number and percentage of treatments that required a prescription change will be computed for each subject by treatment period. The denominator for all percentages will be the number of treatments completed by each subject in the respective treatment period.

Feel Cold and Hypotensive Events

The number and percentage of subjects with at least one reported feel cold event and at least one reported hypotension event will be computed by treatment period. The denominator for all percentages will be the number of ITT subjects.

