5.2 Analysis of Safety Variables

The following describes the safety analyses to be performed for the study. Analysis of the primary safety variable will be performed on the ITT population. All other safety analyses will be performed on the safety population.

Pre-specified Adverse Events for Primary Safety Variable

For each treatment period, a 95% confidence interval will be computed on the pre-specified adverse event rate per dialysis interval. This confidence interval will be computed using the Least Square Mean for the respective treatment period from a generalized linear model containing terms for subject, treatment arm and time points (i.e., a repeated measures analysis using GEE) using a Poisson link function and AR(1) covariance structure. If the AE start date/time is missing, the AE will be counted in the interdialytic interval in which it was observed (if available) or will be randomly assigned (during the final data analysis for the study) to one of the interdialytic periods in the treatment period.

Summary statistics (mean, sample size, standard deviation, minimum, maximum, median) will be computed on the number of pre-specified adverse events per dialysis interval for each treatment period. The same summary

statistics will be calculated by treatment period for the rate of pre-specified adverse events per 100 dialysis treatments.

Additional Analyses of Pre-specified Adverse Events

A table will be provided to show the number and percentage of safety population subjects with at least one pre-specified AE by treatment period and overall for each dialysis treatment interval (treatment, interdialytic, pre-treatment).

A summary table will be constructed to display the following with respect to pre-specified AEs:

- Subjects with at least one pre-specified AE
- Maximum severity, per subject
- Highest relationship to device, per subject
- Highest relationship to treatment, per subject
- Subjects with at least one SAE
- Deaths

All Other Study-Emergent Adverse Events

A table will be provided to show the number and percentage of safety population subjects with at least one study-emergent AE by treatment period and overall for each dialysis treatment interval (treatment, interdialytic, pre-treatment). A similar table will also be provided to show the number and percentage of safety population subjects with at least one occurrence of an AE by categorization (pre-specified AEs or all other AEs) by treatment period and overall.

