Table 16. Summary of Pre-Specified Adverse Events for Primary Safety Endpoint by Treatment Period
 Outset Medical - Study No. 2014-01
 ITT Population (N=xxx)

	Treatment Period	Mean	95% Confidence Interval	Std Dev	n	Min	Max	Median
Number of Pre-Specified Adverse Events Per Dialysis Interval	In-Center	xxx	(xxx, xxx)	xxx	xxx	xxx	xxx	xxx
	In-Home	xxx	(xxx, xxx)	xxx	xxx	xxx	xxx	xxx
Number of Pre-Specified Adverse Events Per 100 Dialysis Treatments	In-Center	xxx	(xxx, xxx)	xxx	xxx	xxx	xxx	xxx
	In-Home	xxx	(xxx, xxx)	xxx	xxx	xxx	xxx	xxx

STATKING Clinical Services (month day, year)
 Source Program: xxxxxxxx.sas

Table 17. Pre-Specified Study-Emergent Adverse Events Summary for Each Treatment Interval by Treatment Period and Overall
 Outset Medical - Study No. 2014-01
 Safety Population (N=xxx)

Treatment Interval	Treatment Period ^a		
	In-Center	In-Home	Overall
Pre-Treatment	xxx (xxx%)	xxx (xxx%)	xxx (xxx%)
Treatment	xxx (xxx%)	xxx (xxx%)	xxx (xxx%)
Interdialytic	xxx (xxx%)	xxx (xxx%)	xxx (xxx%)

^a Counts represent number of subjects with at least one pre-specified study-emergent adverse event with a start date/time in the respective treatment interval and treatment period. The denominator for all percentages is the number of subjects in the safety population.

STATKING Clinical Services (month day, year)
 Source Program: xxxxxxxx.sas

Table 18. Number and Percent of Subjects with Study-Emergent Adverse Events by Treatment Period and Severity, Relationship to Device, Seriousness, and Overall
 Outset Medical - Study No. 2014-01
 Safety Population (N=xxxx)

	Treatment Period ^a		
	In-Center	In-Home	Overall
Subjects with ≥ 1 Adverse Event (AE)	xxxx (xxxx%)	xxxx (xxxx%)	xxxx (xxxx%)
Maximum AE Severity			
Mild	xxxx (xxxx%)	xxxx (xxxx%)	xxxx (xxxx%)
Moderate	xxxx (xxxx%)	xxxx (xxxx%)	xxxx (xxxx%)
Severe	xxxx (xxxx%)	xxxx (xxxx%)	xxxx (xxxx%)
Highest Relationship of AE to Device			
Not Related [n(%)]	xxxx (xxxx%)	xxxx (xxxx%)	xxxx (xxxx%)
Related [n(%)]	xxxx (xxxx%)	xxxx (xxxx%)	xxxx (xxxx%)
Unknown [n(%)]	xxxx (xxxx%)	xxxx (xxxx%)	xxxx (xxxx%)
Highest Relationship of AE to Treatment			
None [n(%)]	xxxx (xxxx%)	xxxx (xxxx%)	xxxx (xxxx%)
Unlikely [n(%)]	xxxx (xxxx%)	xxxx (xxxx%)	xxxx (xxxx%)
Possible [n(%)]	xxxx (xxxx%)	xxxx (xxxx%)	xxxx (xxxx%)
Probable [n(%)]	xxxx (xxxx%)	xxxx (xxxx%)	xxxx (xxxx%)
Definitely [n(%)]	xxxx (xxxx%)	xxxx (xxxx%)	xxxx (xxxx%)
Subjects Experiencing ≥ 1 Serious AE (SAE)	xxxx (xxxx%)	xxxx (xxxx%)	xxxx (xxxx%)

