Pre-Specified Adverse Events	xxx (xxx%)	xxx (xxx%)	xxx (xxx%)
Serious Adverse Event (SAE)	xxx (xxx%)	xxx (xxx%)	xxx (xxx%)
Allergic Reaction	xxx (xxx%)	xxx (xxx%)	xxx (xxx%)
Blood Loss	xxx (xxx%)	xxx (xxx%)	xxx (xxx%)
Hemolytic Reaction	xxx (xxx%)	xxx (xxx%)	xxx (xxx%)
Infection	xxx (xxx%)	xxx (xxx%)	xxx (xxx%)
Intra-Dialysis Event	xxx (xxx%)	xxx (xxx%)	xxx (xxx%)
Vascular Access Complication	xxx (xxx%)	xxx (xxx%)	xxx (xxx%)
Pyrogenic Reaction	xxx (xxx%)	xxx (xxx%)	xxx (xxx%)
All Other Adverse Events	xxx (xxx%)	xxx (xxx%)	xxx (xxx%)

^a Counts represent number of subjects with at least one study-emergent adverse event in the respective category with a start date/time in the respective treatment period. The denominator for all percentages is the number of subjects in the safety population.
 STATKING Clinical Services (month day, year)
 Source Program: xxxxxxxx.sas

Table 22. Summary Table of All Clinical Laboratory Parameters
 Outset Medical - Study No. 2014-01
 Safety Population (N=xxx)

Laboratory Parameter	Data Type ^a	Baseline ^b	In-Center	In-Home
xxx (units)	RAW	xxx	xxx	xxx
	CFB		xxx	xxx
xxx (units)	RAW	xxx	xxx	xxx
	CFB		xxx	xxx
xxx (units)	RAW	xxx	xxx	xxx
	CFB		xxx	xxx
xxx (units)	RAW	xxx	xxx	xxx
	CFB		xxx	xxx
xxx (units)	RAW	xxx	xxx	xxx
	CFB		xxx	xxx

^a All summary data are reported as mean values.

^b Baseline value will be taken as the mean value of all baseline measurements.

STATKING Clinical Services (month day, year)

Source Program: xxxxxxxx.sas

Table 23. Summary Table of Specific Clinical Laboratory Parameters
 Outset Medical - Study No. 2014-01
 Safety Population (N=xxx)

Laboratory Parameter ^c	Data Type	Treatment Period ^a				
		Baseline ^b	In-Center		In-Home	
			Treatments 1-16	Treatments 17-32	Treatments 1-16	Treatments 17-32
xxx (units)	RAW	xxx	xxx	xxx	xxx	xxx
	CFB		xxx	xxx	xxx	xxx
xxx (units)	RAW	xxx	xxx	xxx	xxx	xxx
	CFB		xxx	xxx	xxx	xxx
xxx (units)	RAW	xxx	xxx	xxx	xxx	xxx
	CFB		xxx	xxx	xxx	xxx
xxx (units)	RAW	xxx	xxx	xxx	xxx	xxx
	CFB		xxx	xxx	xxx	xxx
xxx (units)	RAW	xxx	xxx	xxx	xxx	xxx
	CFB		xxx	xxx	xxx	xxx

^a All summary data are reported as mean values.

^b Baseline value will be taken as the mean value of all baseline measurements.

^c Parameters include: platelet count, WBC counts, lymphocytes, lymphocytes %, MID, MID %, GRAN, GRAN %, RBC counts, MCV, MCH, MCHC, RDW, chloride, creatinine, glucose, magnesium, LDH, ferritin, and TSat.

STATKING Clinical Services (month day, year)

Source Program: xxxxxxxx.sas

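### Adverse events outside the eight pre-specified types are reported only as subjects with at least one event, so a frequency difference between In-Center and In-Home is understated

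*Protocol*

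**What the plan says.** Protocol 11.6 sets the counting rule for AE summaries: "Each Subject will be counted only once within a category using the event with the greatest device relationship and greatest severity". SAP 5.2 carries it into the tables for all study-emergent AEs, which show the "number and percentage of safety population subjects with at least one study-emergent AE by treatment period and overall for each dialysis treatment interval". The footnote to SAP Table 21 reads "Counts represent number of subjects with at least one study-emergent adverse event in the respective category". That table puts everything outside the pre-specified list into a single row. Tables 18 and 19 use the same unit, and so does Table 43: "The number and percentage of subjects with at least one reported feel cold event and at least one reported hypotension event" (SAP 4.2.3).

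Frequency is planned for the primary safety variable only: "statistics will be calculated by treatment period for the rate of pre-specified adverse events per 100 dialysis treatments" (SAP 5.2, Table 16). None of the tables listed in SAP 7.0 gives a number of events, or a rate per treatment, for the remaining AEs.

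**The concern.** Each subject is his or her own control for In-Center versus In-Home (Protocol 6.3), and each period has 32 treatments with a signs-and-symptoms questionnaire at every one (Protocol 8.10). AEs can therefore recur within a subject. A count of subjects with at least one AE treats one episode and twenty alike, and it has a ceiling at 100%. The two period columns can then look closer than the underlying event frequencies are. At stake is the description of non-serious, recurrent AEs when care moves from staff to the subject at home.

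**Working it through.** **Inputs**
- Treatments per period: 32. Subjects: 30. Both are in Protocol 11.8 and SAP 1.3.
- Expected rate of AEs outside the list: not given in either document. I assume a range of 0.5 to 20 per 100 treatments. The standard deviation of 0.8 and correlation of 0.50 in Protocol 11.8 apply to pre-specified AEs and cannot supply this rate.
- Size of change: a doubling from In-Center to In-Home, chosen for illustration.

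The plan has no figure of its own for these AEs, so there is none to reproduce.

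**Formulas.** Let r be the rate per treatment and m = 32r the expected AEs per subject per period.
- Common rate: P(at least one) = 1 − exp(−m).
- Subjects who differ, with gamma variation of shape k: P(at least one) = 1 − (1 + m/k)^(−k).

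**Results for a true doubling**

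| AEs per 100 treatments | Common rate | Gap (points) | Ratio shown | Gamma, k = 1 |
|---|---|---|---|---|
| 0.5 to 1 | 14.8% to 27.4% | 12.6 | 1.85 | 13.8% to 24.2% |
| 2 to 4 | 47.3% to 72.2% | 24.9 | 1.53 | 39.0% to 56.1% |
| 5 to 10 | 79.8% to 95.9% | 16.1 | 1.20 | 61.5% to 76.2% |
| 10 to 20 | 95.9% to 99.8% | 3.9 | 1.04 | 76.2% to 86.5% |

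In the last row, 30 subjects × 32 treatments = 960 treatments per period. Events go from 96 to 192, while subjects with at least one AE go from 28.8 to 30.0 of 30.

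**Where the gap is large or small (common rate).** Put x = exp(−m). The gap is x − x².
- Maximum: x = 0.5, gap 25 points, m = 0.693, or about 2.2 per 100.
- Gap of 10 points: x = (1 ± √0.6)/2 = 0.887 or 0.113, so m = 0.120 or 2.183. Dividing by 32 gives 0.37 and 6.8 per 100.
- Gap of 5 points: x = (1 ± √0.8)/2 = 0.947 or 0.053, so m = 0.054 or 2.94, or 0.17 and 9.2 per 100.

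The ratio shown is (1 − x²)/(1 − x) = 1 + exp(−m). It is below 2 at every rate, so a doubling is always understated. The understatement is slight for rare events and near total for frequent ones.

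**With k = 1.** The gap is m/[(1 + m)(1 + 2m)]. Setting it to 0.10 gives 0.2m² − 0.7m + 0.1 = 0, so m = 0.149 or 3.35, or about 0.47 and 10.5 per 100. Between-subject variation therefore moves the upper 10-point threshold from about 6.8 to about 10.5 per 100. It also lowers the largest possible gap to about 17 points (m = 0.707).

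**Information lost (illustration only, since no between-period AE test is planned).** In 4,000 simulated trials of 30 paired subjects at two-sided 5%, I compared an exact McNemar test on any AE with a paired t-test on event counts. Power to detect a doubling:
- 2 per 100: 39% versus 70%
- 5 per 100: 30% versus 97%
- 10 per 100: 0.2% versus 100% (k = 1: 11% versus 99.8%)

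**The case against.** A reader might infer that the subject counts will saturate and that a doubling at home would hardly show. The documents do not support that as a fact. They give no rate, and under a common rate a doubling is visible as 10 to 25 points over a wide band. Several rules also hold the rate down:
- Staff decide whether a reported symptom is an AE (Protocol 9.2.1).
- Only new or worsened events count (9.2.2).
- Some dialysis-related events can be classed as Additional Treatment Observations instead (6.4, 9.1.3).
- Subjects with recent recurrent symptomatic intradialytic hypotension are excluded (7.5, criterion 9).

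Splits by severity, relationship or sub-interval have lower rates than the total and saturate less. All of this stands.

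Nor do home-related problems disappear from view. Access infections, vascular access complications and pyrogenic reactions are on the pre-specified list and get rates. Alarms, including low systolic pressure, are tabulated per treatment (Tables 34 to 39). However, Protocol 9.1.3 classes alarms as observations rather than AEs, so they do not fill the gap for AEs.

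A reader might also take the aim in Protocol 9.2.1, to "eliminate any potential observed differences in AE rates between the study arms", as a promise to compare event rates. The sentence goes on to limit itself to differences that arise from how events are reported. It concerns ascertainment bias, and the word rates there could mean subject incidence.

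Finally, the rule in Protocol 11.6 asks for one event that is greatest on both relationship and severity. No such event need exist for a subject with a severe unrelated AE and a mild related one. The SAP largely settles this by tabulating the two maxima separately. What remains is that severe device-related AEs cannot be read from Tables 18 and 20.

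**Conclusion.** The point holds as a gap in reporting. AEs outside the eight pre-specified types have no planned event count or rate, and the planned percentage understates any difference in frequency between periods.

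The size is conditional. Under a common rate and 32 treatments in each period, a doubling shows as 10 to 25 points at about 0.4 to 6.8 AEs per 100 treatments, and as less than 10 points above that, which is about 2.2 AEs per subject per period. With strong variation between subjects (k = 1), 10 versus 20 per 100 still shows about 10 points. Which part of the range applies cannot be settled from the documents. No success criterion in Protocol 11.3 depends on these tables, so the trial's formal conclusion is unaffected. What suffers is the description of AE frequency at home.

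**What to change.** In Protocol 11.6 and SAP 5.2, keep the subject counts. For each period in Tables 18, 19 and 21, add the number of events and the events per 100 treatments delivered in that period. Give a 95% CI clustered on subject for total AEs, for example from a Poisson GEE with log treatments delivered as offset, in line with the GEE already planned for the primary safety variable.

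Optionally, add one row to Tables 18 and 20 for maximum severity among device-related AEs, with unknown relationship treated as related, as Protocol 9.2.3 requires.

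The cost is wording in both documents, two extra columns per period and at most one row. No new data are needed: Table 19 already needs the timing of each AE, and treatments are already counted for Tables 16 and 34. The small downside is longer tables, and the In-Home figures may look less favourable.

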11.7 Interim Analysis

No formal statistical interim analyses will be conducted during this study.

11.8 Sample Size Analysis

The estimated sample size for the trial was based on the safety endpoint and yields an estimate of the rate of pre-specified adverse events per 100 dialysis treatments in each treatment period (In-Center and In-Home use), to a margin of error of less than 1 event per 100 treatments. With a two-sided α =0.05, in order to construct a 95% confidence interval on the rate of pre-specified adverse events per 100 dialysis treatments with half-width less than 1 event per 100 treatments, the sample size required would be n=30 Subjects with 4 dialysis intervals per week for a minimum of 8 weeks (i.e., 30 subjects with a minimum of 32 treatments). The sample size calculation was based on an asymptotic normal theory one sample test using variance estimates that included covariance terms for repeated measurements (4 dialysis intervals per week for 8 weeks) on each Subject with a block diagonal first order autoregressive (AR(1)) covariance structure. This sample size calculation assumed a standard deviation of 0.8 AEs per dialysis interval and a within Subject correlation of pre-specified AE counts of ρ =.50.

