11.3 Analysis of Primary Endpoint

The study is based on the primary endpoints for effectiveness and interval estimates of the safety of the device. The study will be considered a success from a statistical standpoint if:

- 1. Both primary analysis variables pass their respective hypotheses, i.e., H_{a0} and H_{b0} below are rejected in favor of H_{a1} and H_{b1}, respectively,
- 2. The rate of pre-specified adverse events per dialysis interval is estimated to be within the specified error of estimation for each treatment period.

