1.3 Sample Size

The sample size for the study is based on the primary effectiveness endpoint, weekly standardized Kt/V and the primary safety endpoint, the number of pre-specified, serious, device related, treatment emergent adverse events during a dialysis interval.

A hypothesis test that the treatment period mean weekly standardized Kt/V is statistically significantly greater than 2.1 will be carried out for both the In-Center and In-Home treatment periods. Given that the true treatment period mean Kt/V is 2.5 units, with one-sided $\alpha=0.025$, a sample size of $n=11$ subjects, each measured weekly for at least 8 weeks of treatment, will have >90% power to detect that the mean is statistically significantly greater than 2.1 in the treatment period. This sample size calculation assumed a standard deviation of 0.7 units,

based on Sands et al (2009)¹, and a within patient correlation of Kt/V values of $\rho=.50$. The sample size calculation was based on an asymptotic normal theory one sample test using variance estimates that included covariance terms for repeated (weekly) measurements on each patient with a block diagonal first order autoregressive (AR(1)) covariance structure.

For the safety endpoint, the needed sample size yields an estimate of the rate of pre-specified adverse events per 100 dialysis treatments in each treatment period (In-Center and In-Home use), to a margin of error of less than 1 event per 100 treatments. With a two-sided $\alpha=0.05$, in order to construct a 95% confidence interval on the rate of pre-specified adverse events per 100 dialysis treatments with half-width less than 1 event per 100 treatments, the sample size required would be $n=30$ subjects with 4 dialysis intervals per week for a minimum of 8 weeks (i.e., 30 subjects with a minimum of 32 treatments). The sample size calculation was based on an asymptotic normal theory one sample test using variance estimates that included covariance terms for repeated measurements (4 dialysis intervals per week for 8 weeks) on each patient with a block diagonal first order autoregressive (AR(1)) covariance structure. This sample size calculation assumed a standard deviation of 0.8 AEs per dialysis interval and a within patient correlation of pre-specified AE counts of $\rho=.50$.

Given the sample sizes necessary to satisfy the power requirements for the Kt/V endpoint and the composite safety endpoint, a sample size of $n=30$ subjects will be needed for the study.

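### The stated safety sample-size inputs give a 95% half-width of about 8.6 events per 100 treatments at n=30, not less than 1

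*Protocol*

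**What the plan says.** Protocol 11.8 bases the sample size on the safety endpoint. The aim is a 95% confidence interval, in each treatment period separately, "with half-width less than 1 event per 100 treatments, the sample size required would be n=30 Subjects" with 4 dialysis intervals per week for at least 8 weeks, that is at least 32 treatments each. The method is a normal-theory one-sample calculation with a block diagonal AR(1) covariance. On the inputs: "This sample size calculation assumed a standard deviation of 0.8 AEs per dialysis interval", with a within-subject correlation of .50. SAP 1.3 repeats the same inputs and the same result.

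SAP 1.3 also gives a Kt/V calculation by the same method: with SD 0.7, correlation .50, a true mean of 2.5 against 2.1 and one-sided α=0.025, it finds that 11 "subjects, each measured weekly for at least 8 weeks of treatment, will have >90% power". The section then combines the two: "Given the sample sizes necessary to satisfy the power requirements for the Kt/V endpoint and the composite safety endpoint", 30 subjects are needed.

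Protocol 11.3 makes precision a condition of study success: "The rate of pre-specified adverse events per dialysis interval is estimated to be within the specified error of estimation for each treatment period". It gives no number for that error. Protocol 11.6 describes the interval to be reported: "For each treatment period, a 95% confidence interval will be computed on the pre-specified adverse event rate per dialysis interval".

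**The concern.** A target of 1 event per 100 treatments is 0.01 events per interval. The assumed SD is 0.8 per interval, 80 times larger. To bring 1.96 standard errors down to 0.01, the 960 intervals in a period would have to carry far more information than they do, and positive correlation within subjects reduces it further.

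Two things rest on the statement. First, it is the only justification for 30 subjects, since Kt/V needs 11. Second, the less-than-1-per-100 figure is the only precision figure in either document, so it is apparently the error that the Protocol 11.3 success condition refers to. If the figure is unsupported, so is the stated reason for the trial's size, and the success condition has no sound number behind it.

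**Working it through.** **Inputs** (Protocol 11.8, repeated in SAP 1.3): n = 30 subjects; m = 32 intervals per period; SD = 0.8 events per interval; ρ = 0.50, AR(1); two-sided 95% interval, z = 1.96; target half-width below 0.01 per interval.

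**Formula.** The variance of a subject's mean over m AR(1) measurements is SD² × F(m)/m, where F(m) = 1 + 2 Σₖ₌₁^(m−1) (1 − k/m) ρᵏ. For n subjects, SE = SD × √(F/(n m)), and the half-width is 1.96 × SE.

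**Step 1: reproduce the plan's own Kt/V figure.** SD 0.7, m = 8 weeks, ρ = 0.50, difference 2.5 − 2.1 = 0.4. F(8) = 2.502. Power = Φ(0.4/SE − 1.96), with SE = √(0.49 × 2.502/(8n)).
- n = 10: SE = 0.1238, power 89.8%.
- n = 11: SE = 0.1180, power 92.3%.

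Eleven is the smallest n above 90%, as SAP 1.3 states. The formula is therefore the one that the SAP describes and used for Kt/V.

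**Step 2: apply it to safety.** F(32) = 2.875. SE = √(0.64 × 2.875/960) = 0.0438. Half-width = 1.96 × 0.0438 = 0.0858 per interval, or **8.58 per 100 treatments**. Summing the full 32 × 32 AR(1) covariance matrix gives the same 8.58.

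**Step 3: more generous readings with SD 0.8.** If the blocks are weeks, F(4) = 2.0625. Independence has F = 1. Required n is (1.96 × 0.8/0.01)² × F/32.

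| Covariance reading | Half-width per 100, n=30 | Half-width per 100, n=50 | n for 1 per 100 |
|---|---|---|---|
| AR(1) over 32 intervals | 8.58 | 6.65 | 2,209 |
| AR(1) within weeks | 7.27 | 5.63 | 1,585 |
| Independent | 5.06 | 3.92 | 769 |

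Fifty is the enrolment maximum in the Protocol synopsis. Other departures from the stated calculation do not reach 1 either: pooling both periods (64 intervals) gives 6.13, a one-sided z gives 7.20, and taking the SE alone in place of the half-width gives 4.38.

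**Step 4: the SD that would fit.** With n = 30 and a target of 0.01, the largest SD is 0.01 × √(960/F)/1.96 = 0.093 (AR(1)), 0.110 (weekly blocks) or 0.158 (independent).

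**Step 5: is there an obvious slip?** An SD of 0.08 with the stated target, or an SD of 0.8 with a target of 10 per 100, needs n = 23 (AR(1)), 16 (weekly blocks) or 8 (independent). Reading 0.8 as the SD of a subject's total over 32 treatments (0.8/32 = 2.5 per 100) needs (1.96 × 2.5)² = 24.01, so 25. None gives 30, and the documents support none of them.

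**Step 6: when could 30 subjects still meet ±1?** If the variance equals the mean (an assumption, not in the plan), the planning formula is met for true rates up to the squares of the SDs in step 4: about 0.9, 1.2 and 2.5 per 100 under the three readings.

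**The case against.** The arithmetic is not open to dispute, and the same SD appears in both documents, so a text-extraction fault is unlikely. The strongest objections concern the consequences.

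- **The success condition is linked to 11.8 only by inference.** Protocol 11.3 speaks of a rate per interval and an unnamed error, while 11.8 gives a planning margin per 100 treatments. No passage equates them, and SAP 5.2 has no pass/fail rule on precision. This stands, so the link can only be called apparent. The missing number in 11.3 would be a gap even if 11.8 were right.
- **The trial's results may be untouched.** The reported interval uses observed counts, and Kt/V power at n = 30 exceeds 99.9% on the plan's assumptions. This also stands. The defect is in the justification of n and in the stated precision, and a low event rate could still meet ±1.
- **The rates in step 6 are planning-formula values.** The reported interval comes from a Poisson GEE. If that means a log link with back-transformed limits (an assumption), half the total width under AR(1) over 32 intervals never falls below about 1.04 per 100 at n = 30. The upper rate limit becomes about 0.9 under weekly blocks and 2.4 under independence. The rates in step 6 are therefore indicative only.
- **The slip check is speculative.** It shows only that none of the simple slips tried recovers n = 30. It does not identify the cause.

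None of this reconciles SD 0.8 with a half-width below 1.

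**Conclusion.** The concern holds. As written, the safety sample-size statement is wrong by a factor of about 8.6 under the stated AR(1) assumptions, and by a factor of about 5 under the most favourable covariance reading in the table. This rests only on inputs printed in Protocol 11.8 and SAP 1.3 and on a formula that reproduces the SAP's own Kt/V result. Which of SD, target or unit is in error cannot be told from the documents. The stated basis for n = 30 is unsupported, and so apparently is the precision behind the second success condition in Protocol 11.3. It does not follow that 30 subjects are too few: that depends on the true variability, which the documents do not establish. It must be corrected because the error is in both governing documents and is the only calculation that yields 30.

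**What to change.** Reconcile SD, units, target half-width and n in Protocol 11.8 and SAP 1.3:

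- If SD 0.8 per interval is right, state the precision that 30 subjects give, about ±8.6 per 100 treatments under AR(1).
- If it is a misprint, give the SD actually used and its source, and show that it leads to n = 30.
- If the target or its unit is wrong, correct it.
- Say whether the AR(1) blocks are subjects over 32 intervals or weeks within subjects.

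Then put the numeric error and its unit into item 2 of Protocol 11.3, with a reason why that precision is adequate. It should not simply be set to whatever n = 30 delivers.

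A separate wording point, with no effect on the arithmetic: SAP 1.3 describes the safety endpoint as "the number of pre-specified, serious, device related, treatment emergent adverse events during a dialysis interval", whereas SAP 5.1 and Protocol 5.2 count every event on the pre-specified list. Align the wording in the same edit.

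The cost is text changes to Protocol 11.3 and 11.8 and SAP 1.3, with no added patients, visits or data. The stated precision may become less favourable.
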